Title	The MiniMed™ 780G Glycemic Control and Quality of Life study for the treatment of pediatric and adult subjects with Type 1 Diabetes in France. (EQOL Study)
Clinical Study Type	Post-Market non-interventional, prospective, local, single-arm, multi-center non-randomized study
Product Name	
 • MiniMed™ 780G Pump labelled as MiniMed™ Insulin Pump (MMT-1896WWA) - referred to as MiniMed™ 780G Pump throughout the protocol • Guardian™ Link (3) Transmitter Kit (MMT-7910W1) • Guardian™ Sensor (3) Glucose Sensor (MMT-7020D1, MMT-7020C1), referred to as Guardian Sensor (3) throughout this protocol • One-Press Serter (MMT-7512W) -referred to as the Serter throughout the protocol • Accu-Chek® Guide Link Blood Glucose Meter - ROCHE Accu-Chek® (08116083016M)- referred to as the Study Meter throughout this protocol) • MiniMed Reservoir (MMT-332A; MMT-326A) • Infusion sets table list of compatible infusion sets is in table 2. • Activity Guard (ACC-1520) • MiniMed Mobile app (MMT-6101 for Android; MMT-6102 for iOS) • CareLink BLE USB [Blue Adaptor] (ACC-1003911B) • Medtronic CareLink™ Personal for Clinical Research Therapy Management Software (MMT-7338) 
Note: upload of MiniMed™ system data will be done via Medtronic CareLink™ Personal for Clinical Research Therapy Management Software until the mobile app is available.
 
Medtronic may incorporate additional/updated devices, software and accessories into this clinical study as they receive appropriate license or regulatory approval and are released commercially by Medtronic.

Sponsor/Local Sponsor	
Medtronic France SAS
 
[REDACTED]
 
[REDACTED]
 
The sponsor will maintain a list of staff under a separate cover

Indication under investigation	Subjects, 7 years of age and older, with Type 1 Diabetes mellitus (T1D) under Continuous Subcutaneous Insulin Infusion (CSII) therapy ≥6 months with or without Continuous Glucose Monitoring (CGM).
Investigation Purpose	To evaluate the efficacy in glycemic control and the impact on the quality of life of patients using the MiniMed™ 780G System for the treatment of Type 1 diabetes, in real life settings in France.
Product Status	All products have obtained CE mark.
Primary Objective(s)	To evaluate if the MiniMed™ 780G system in Auto Mode increases the proportion of Time In Range (TIR) at 6 months compared to MiniMed™ 780G system in Manual mode (with no SmartGuard™ functions) at baseline. TIR is defined as percentage of sensor glucose values within 70-180mg/dL.
Secondary Objective(s)	
Secondary Objective #1: To assess the change of the TIR at baseline and every three months until 12 months.
 
Secondary Objective #2: To evaluate the change from baseline in satisfaction score based on the DTSQc evaluated at 6 months.
 
Secondary Objective #3: To evaluate the change from baseline in quality of life based on the DQoL evaluated at 6 and 12 months.
 
Secondary Objective #4: To evaluate the change from baseline in the fear of hypoglycemic events based on the HFS evaluated at 6 and 12 months.
 
Secondary Objective #5: To evaluate the change of glycemic parameters at baseline and every three months until 12 months and the change in HbA1c from baseline to 6 months and 12 months.
 
Secondary Objective #6: To evaluate the treatment satisfaction score based on the DTSQs evaluated at baseline, 6 and 12 months

Study Design	Local, post-market, non-interventional, prospective, single-arm, multi-center study of patients (Pediatric and adult).
Sample Size	Approximately 300 patients (children and adults) in approximately 32 sites in France.
Duration	It is foreseen that the enrollment period will last for 12 months. The follow up of the patients is of maximum 1-year post Auto Mode activation after baseline visit. Each subject will enter a run-in phase (baseline) in hospital outpatient setting of approximately 2 weeks as per standard clinical practice, followed by a study period of 12 months. Therefore, the maximum duration of subject participation in the study is approximately 12 months. The total study duration is expected to be 2 years.

Medtronic Controlled Information

Inclusion/Exclusion Criteria	Inclusion	Exclusion
	
1. Subject is ≥ 7 years of age.2. Subject has a clinical diagnosis of type 1 diabetes for more than 1 year as determined via medical records or source documentation by an individual qualified to make a medical diagnosis.3. Subject has a glycosylated haemoglobin (HbA1c) value greater than 6.5% and less than 12% at time of enrolment visit.4. Subject is under Continuous Subcutaneous Insulin Infusion (CSII) therapy (with or without Continuous Glucose Monitoring) for 6 months or more before enrolment.5. Subject requires ≥ 8 units of insulin per day.6. Subjects and their parent(s)/guardian(s) must be able to speak and be literate in French as verified by the investigator.7. Subjects and their parent(s)/guardian(s) are willing to participate in the study and sign the DRF8. Subjects who are ≥ 18 years of age should be able to provide consent	
1. Subject has MiniMed™ 780G System IFU contraindication(s).2. Subject used Predictive Low-Glucose Management (PLGM) System (i.e. MiniMed™ 640G with SmartGuard™) in the last 6 months before the enrolment.3. Subject used Low Glucose suspend (LGS) feature (i.e. MiniMed™ Paradigm Veo Pump) in the last 6 months before the enrolment.4. Subject under Multiple Daily Injections (MDI) treatment in the 6 months before the enrolment.5. Subject has any unresolved adverse skin condition in the area of sensor placement (e.g., psoriasis, dermatitis herpetiformis, rash, hylococcus infection).

Study Procedures and Assessments	
Data will be collected as follow:
 
Baseline
 
Demographics at Baseline: age, gender. Medical history at Baseline: HbA1c, Previous treatment, Name of the last pump device, Date of the first pump treatment, Number of severe hypoglycemia events in the last year, years since diagnose of T1D; DTSQs; DQoL; HFS. Auto Mode Activation at Baseline: Auto Mode activation date At the end of the run-in period, the following data will be also collected: Mean TIR (70-180mg/dL); Mean Time spent of sensor glucose value below 70mg/dL and below 54mg/dL; Mean Time spent of sensor glucose value above 180mg/dL and above 250mg/dL; Number of bio-chemical hypoglycemic event per week.
 
6M
 
DTSQs and DTSQc; DQoL; HFS; Diabetes parameters via CareLink™ Personal for Clinical Research: TIR; Mean time spent of sensor glucose value below 70mg/dL and below 54mg/dL; Mean time spent of sensor glucose value above 180mg/dL and above 250mg/dL; Number of bio-chemical hypoglycemic event per week; HbA1c Number of severe hypoglycemia; Use of Auto Mode; Use of CGM; Number of Auto Mode outings.
 
12M
 
DTSQs; DQoL; HFS; Diabetes parameters via CareLink™ Personal for Clinical Research: TIR;

---	--

	
Mean time spent of sensor glucose value below 70mg/dL and below 54mg/dL; Mean time spent of sensor glucose value above 180mg/dL and above 250mg/dL; Number of bio-chemical hypoglycemic event per week; HbA1c Number of severe hypoglycemia; Use of Auto Mode; Use of CGM; Number of Auto Mode outings.
 
Device data (insulin/CGM) will be collected throughout the study period and evaluated at every 3month.

Safety Assessments	Post-Market surveillance applies only. Adverse Events and Device Deficiencies are not collected. This is an efficacy and Quality of Life and treatment satisfaction non-interventional study. Complaint reporting will be done as per local requirements and Medtronic processes, including vigilance for commercially approved products.
Statistics	
The sample size was determined using a one sample paired test assuming a one- sided type I error rate of 0.05 and power greater than 90%. The TIR at baseline is assumed to be around 60% and the TIR at 6 months follow up is assumed to be 63% with standard deviation as 16% and a correlation as 0.5. The sample size needed to demonstrate this hypothesis including 20% of attrition rate is 306.
 
Descriptive statistics will be used to summarize patient characteristics. For categorical variables, the description will consist in frequency and the percentage of each category. For continuous variables, the description will consist summary statistics as mean, standard deviation, standard error, minimum, median and maximum.
 
The primary endpoint on efficacy defined as the change of TIR at 6 months from Auto Mode activation will be analyzed by means of paired (samples) t-test or Wilcoxon signed rank sum test according to the normal or non-normal distribution.
 
The primary outcome will include all patients as the ITT population. Sensitivity analysis will include the per protocol patients as defined by >70% Auto Mode usage.

4. Introduction

4.1. Background

The Medtronic MiniMed™ sensor augmented insulin pumps have been helping insulin requiring patients with diabetes mellitus all around the world for more than two decades. In order to address some of the unmet needs of these patients and to provide them the benefits of newer technologies, Medtronic Diabetes has developed a new Sensor Augmented Pump platform: the MiniMed™ 780G System, also referred as Advanced Hybrid Closed Loop system.

In patients with insulin dependent diabetes mellitus, glycemic control is influenced by numerous factors, such as insulin dosage, insulin absorption, timing, physiological/lifestyle factors such as exercise, food intake, hormones and illness. These factors may contribute to significant variability in insulin requirements, which makes self-management of type 1 diabetes challenging.

Patients who are using continuous glucose monitoring, including sensor-augmented pump therapy, experience improvements in glycemic control. Advanced features of sensor-augmented pump therapy are now being used in clinical practice; these include automatic suspension of insulin delivery when a pre-set glucose threshold is reached (suspend on low) or is predicted to be reached (suspend before low). Both approaches have shown that a significant reduction in the risk and burden of hypoglycemia can be achieved, especially in patients who are prone to experiencing hypoglycemia. Parallel to these approaches to mitigate the risk of hypoglycemia, more progressive advancements in technology can link insulin delivery directly to glucose levels. Closed-loop insulin delivery is different from conventional pump therapy and low glucose management technology, because it uses a control algorithm to automatically adjust insulin delivery based on subcutaneous sensor data to improve diabetes management. Manual meal-time announcement and prandial insulin boluses still need to be carried out by patients in order to overcome the delay in insulin action of currently available insulin analogues administered subcutaneously. The 'hybrid' closed-loop approach contrasts with a 'fully' closed-loop approach, in which user input to the control algorithm related to meals would no longer be required.

Medtronic has conducted numerous studies to evaluate hybrid closed loop (HCL) technology, currently used in the MiniMed™ 670G System.

The HCL System consists of an insulin pump that delivers insulin to the user, a continuous glucose monitor (CGM) including algorithm that measures the user's glucose levels for up to seven days, and a glucose meter used to calibrate the CGM. The MiniMed™ 670G System is able to decrease or stop insulin delivery when it detects the user's glucose is low or increase the insulin delivery when the system detects the user's glucose levels are high with no input from the user.

After completing a variety of feasibility studies with the hybrid closed loop algorithm, two separate pivotal trials were initiated to show that the use of hybrid closed loop technology (MiniMed™ 670G

System) is safe in both adults and children over the age of 2. In the young adult/adult pivotal study, patients aged 14 to 75 years with type 1 diabetes were recruited from 10 centers (9 in the United States, 1 in Israel). The pediatric pivotal study was conducted as an at-home, multi-center study, which enrolled participants ages 2-13 years. Patients were recruited at 11 centers (10 in the United States, 1 in Israel). The study was identical in design to the young adult/adult pivotal study.

Study results in the pediatric study mirrored data from the pivotal trial of the system in adults and adolescents (14 and above), showing patients spent more time in euglycemic range, experienced less glycemic variability, had less exposure to hypoglycemia and hyperglycemia and significantly reduced HbA1c compared to baseline data, where they used sensor-augmented pumps. No episodes of severe hypoglycemia or diabetic ketoacidosis and no serious device-related adverse events were reported.

The Advanced Hybrid Closed Loop system (AHCL) is based on the MiniMed™ 670G hybrid closed loop system currently in commercial distribution in the United States, Canada and Europe. Relative to the MiniMed™ 670G system, AHCL includes enhancements intended to reduce the frequency of Auto Mode exits and decrease the time spent in hyperglycemia. Advancement such as automatic correction bolusing, sensor glucose based meal bolusing, automatic calibrations of Blood Glucose (BG) measurements transmitted to the pump and a variable target for automatic basal deliveries, all maximize the time spent in hybrid closed-loop operation, in order to further improve glucose control and overall user satisfaction.

Patients using the AHCL system will not be required to confirm sensor glucose using SMBG (Self-Monitoring of Blood Glucose) measurement before making therapy adjustments based on displayed sensor glucose values.

The advanced algorithm receives continuous glucose monitoring (CGM) data every 5 minutes, and a “basal rate” insulin delivery is computed and adjusted every five minutes. Therefore, standard “basal” insulin that is pre-programmed in regular insulin pump therapy is replaced by the algorithm derived insulin delivery (given as a micro-bolus every 5 minutes).

Meals will be announced, and sensor glucose based insulin bolus for a meal will be delivered according to the individualized patient carbohydrate ratio and insulin sensitivity factor.

The MiniMed 780G system is intended for the continuous delivery of basal insulin at selectable rates, and the administration of insulin boluses at selectable amounts. The system is also intended to continuously monitor glucose values in the fluid under the skin. The MiniMed 780G system includes SmartGuard technology, which can be programmed to provide an automatic adjustment of insulin delivery based on continuous glucose monitoring (CGM) and can suspend the delivery of insulin when the SG value falls below, or is predicted to fall below, predefined threshold values.

The MiniMed™ 780G system received CE (Conformité Européenne) Marking in June 2020. While in the United States, the MiniMed™780G system is for investigational use only, and not approved for

sale or distribution.

Several clinical studies were conducted (Table 1) to demonstrate the safety and effectiveness of the MiniMed™ 670G and 780G Systems. However, data regarding the effect on glycemic control, quality of life and treatment satisfaction of MiniMed™ 780G System under the routine practice in France are highly recommended by the French National Authority for Health (HAS).

Table 1: Clinical Program MiniMed™ HCL and AHCL Systems

Study	Sponsor	Design	Population	System	Manuscript
Hybrid Closed Loop Pivotal Trial in Type 1 Diabetes NCT02463097	Medtronic	Pivotal trial (US and Israel)	Age 14-75	HCL	Published by Garg et al. "Glucose Outcomes with the In-Home Use of a Hybrid Closed-Loop Insulin Delivery System in Adolescents and Adults with Type 1 Diabetes" Diabetes Technol Ther. 2017 Mar;19(3):155-163. doi: 10.1089/dia.2016.0421. Epub 2017 Jan 30.
Safety Evaluation of the Hybrid Closed Loop (HCL) System in Pediatric Subjects with Type 1 Diabetes NCT02660827	Medtronic	Interventional, non-randomized, single-arm, multicenter trial (US and Israel)	Age 2-13	HCL	Published by Forlenza et al. "Safety Evaluation of the MiniMed™ 670G System in Children 7-13 Years of Age with Type 1 Diabetes." Diabetes Technol Ther. 2019 Jan;21(1):11-19. doi: 10.1089/dia.2018.0264. Epub 2018 Dec 26.
Multi-center Trial in Adult and Pediatric Patients With Type 1 Diabetes Using Hybrid Closed Loop System and Control at Home NCT02748018	Medtronic	Interventional, randomized controlled trial (RCT) (US, Canada, Europe)	Age 2-80	HCL	Ongoing recruitment

Medtronic Controlled Information

Safety Evaluation of the Advanced Hybrid Closed Loop (AHCL) System in Type 1 Adult and Pediatric Subjects G190075	Medtronic	Interventional, non-randomized, multi-center, single arm (US)	Age 7-75	AHCL	Completed 2020
ADAPT ADvanced Hybrid Closed Loop study in Adult Population with Type 1 Diabetes: A Prospective, Open-label, Multi-center, Adaptive, Confirmatory and Randomized Controlled Study	Medtronic	Pre-market. Prospective, Open-label, Multi-center, Adaptive, Confirmatory and Randomized Controlled Study (EMEA)	Age \geq 18	AHCL	Ongoing recruitment

4.2. Purpose

Medtronic France SAS is sponsoring the CIP328 EQOL study, a Post-Market non-interventional, prospective, local, single-arm, multi-center non-randomized clinical study. The purpose of this study is to evaluate the impact on glycemic control and quality of life of patients using the MiniMed™ 780G System for the treatment of Type 1 diabetes, in real life settings in France to support reimbursement of the MiniMed™ 780G in France. This data will complete the available data from international pivotal studies, as it is highly recommended by the French authorities to provide local data on glycemic control, quality of life and treatment satisfaction in real life conditions.

5. Objectives and Endpoints

5.1. Primary Objective and Endpoint

The primary objective is to evaluate if the treatment of T1D with MiniMed™ 780G System in pediatric and adult population increases the Time In Range (TIR) at 6 months compared to MiniMed™ 780G System in Manual Mode (with no SmartGuard™ functions) during the run-in period (expected to be approximately 2 weeks). TIR is defined as time spent of sensor glucose values within 70-180mg/dL.

The primary endpoint is the change in (%) the time spent within range (TIR) defined as the proportion of sensor glucose concentration within the target range 70-180 mg/dL (3.9-10.0 mmol/L) between baseline and 6 months.

5.2. Secondary Objectives and Endpoints

Secondary objectives will aim at evaluating the difference in time in range, quality of life and treatment satisfaction.

- 1) Secondary objective #1: To assess the change of the TIR collected at baseline and every three months until 12 months
- 2) Secondary Objective #2: To evaluate the change from baseline in satisfaction score based on the DTSQc evaluated at 6 months.
- 3) Secondary Objective #3: To evaluate the change from baseline in quality of life based on the DQoL evaluated at 6 and 12 months.
- 4) Secondary Objective #4: To evaluate the change from baseline in the fear of hypoglycemic events based on the HFS evaluated at 6 and 12 months.
- 5) Secondary Objective #5: To evaluate the change of glycemic parameters at baseline and every three months until 12 months and the change in HbA1c from baseline to 6 months and 12 months.
- 6) Secondary Objective #6: To evaluate the treatment satisfaction score based on the DTSQs evaluated at baseline, 6 and 12 months

Secondary Endpoints:

- a) Secondary endpoint #1: The Time In Range (TIR) defined as the proportion of sensor glucose concentration within the target range of 70-180 mg/dL (3.9-10.0 mmol/L) every 3 months.
- b) Secondary Endpoint #2: The different DTSQc versions will be used to assess satisfaction in the following populations:
 - a. DTSQc Adult (≥ 18 years old)
 - b. DTSQc Teen (13-17 years old)
 - c. DTSQc Parent (7-12 years old)
- c) Secondary Endpoint #3: the DQOL questionnaire will be used and the mean scores will be compared between baseline and 6 and 12 months. The different DQOL versions will be used

to assess quality of life in the following populations:

- a. DQOL Adult (≥ 18 years old)
- b. DQOL Adult with Adolescent-oriented items (13-17 years old)
- c. No DQOL version and therefore collection for patients 7-12 years old
- d) Secondary Endpoint #4: the HFS questionnaire will be used and the mean scores will be compared between baseline and 6 and 12 months. The different HFS versions will be used to assess the fear of hypoglycemic events in the following populations:
 - a. HFS Adult (≥ 18 years old)
 - b. HFS Teen (13-17 years old)
 - c. HFS Parent (7-12 years old)
- e) Secondary Endpoint #5: The time of sensor glucose values below 70mg/dL and below 54mg/dL, time of sensor glucose values above 180mg/dL and above 250mg/dL at baseline and every 3 months. The change in HbA1c from baseline to 6 and 12-month follow up.
- f) Secondary Endpoint #6: The different DTSQs versions will be used to assess satisfaction in the following populations:
 - a. DTSQs Adult (≥ 18 years old)
 - b. DTSQs Teen (13-17 years old)
 - c. DTSQs Parent (7-12 years old)

6. Study Design

This study is a local, post-market, non-interventional, prospective, single-arm, multi-center, non-randomized study assessing the glycemic control effect, treatment satisfaction and the quality of life of patients using MiniMed™ 780G System as per the standard care of practice. This study has a single-arm design which will recruit a maximum of 300 subjects in up to 32 sites in France. At the time of Clinical Investigational Plan finalization, the list of participating sites was not finalized. The complete list, which includes the name, position, address and contact details of the investigators responsible for conducting the study for each investigational site, will be available under separate cover and provided to the sites.

To avoid introduction of bias to the study results due to disproportionate enrollment, enrollment at any individual site should not exceed 10% (30 subjects) of the total sample size. It's expected that sites enroll a minimum of 10 subjects per site.

Enrollment will be competitive across study sites. The per-study site enrollment cap may be increased upon Sponsor approval.

[figure not shown]
Subject enrolled in this study (or his/her parent/legal representative in case of DTSQ and HFS for patients 7-12 years old) will be asked to complete the questionnaires DTSQ, DQOL (if patient is ≥ 13 years old) and HFS at baseline/enrollment visit and at 6- and 12- month follow-up visits.

The following measures are taken to minimize potential sources of bias:

- A multi-center design is used to ensure a representative sample of physicians providing the

- treatment and to reach a reasonable enrollment period.
- Site selection will be done per predefined selection criteria.
 - Only physicians that have adequate documented experience in diabetes management will participate.
 - Site training is performed according the training & education plan set up for the pump use in order to assure full understanding and engagement to comply with the pump best utilization.
 - Consecutive screening and enrollment will be encouraged and enforced as much as possible.

Figure 1: Study design overview

CareLink™ Personal for Clinical Research data uploads from the devices should be done via Bluetooth connectivity or via USB connection as per clinical practice, i.e. once a week. CareLink™ Data evaluation will be done every 3 months.

Duration

It is foreseen that the enrollment period will last for 12 months. The follow up of the patients is of maximum 1 year post Auto Mode activation in baseline visit. Each subject will enter a run-in phase in hospital outpatient setting of approximately 2 weeks as per standard clinical practice, followed by a study period of 12 months. Therefore, the maximum duration of subject participation in the study is of approximately 12 months. The estimated study duration is 2 years.

Medtronic Controlled Information

[figure not shown]

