12.1. Sample size justification

The primary endpoint is to evaluate if the MiniMed™ 780G therapy in Auto Mode increases the proportion of Time In Range (TIR) at 6 months compared to the MiniMed™ 780G therapy in manual mode at baseline. The endpoint is the Time In Range (TIR) defined as the proportion of sensor glucose concentration within the target range 70-180 mg/dL (3.9-10.0 mmol/L).

The Pivotal study [12, 13] enrolled adolescents (ages 14–21 years) and adults (ages 22–75 years) with type 1 diabetes in a multicenter pivotal trial. The Medtronic MiniMed™ 670G system was used during a 2- week run-in phase without HCL control, or Auto Mode, enabled (Manual Mode) and, thereafter, with Auto Mode enabled during a 3-month study phase. The study has shown a significant

improvement on TIR of 60.4% (10.9%) to 67.2% (8.2%) in adolescents and from 68.8% (11.9%) to 73.8% (8.4%) in adults. Using this information and considering that this study is expected to include around 32 sites and including also patients aged >7 years old, a lower increase of TIR and higher variability are expected. The following assumptions were made:

- Improvement in TIR of at least 3% points at 6 months compared to the baseline.
- Standard deviation as 16% due to the mixed population and multiple sites expected for this study.

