12.2. Sample size Calculations

The sample size was determined using a one sample paired test assuming a one-sided type I error rate of 0.05 and a power greater than 90%. The TIR at baseline is assumed to be 60% and the TIR at 6 months follow up (TIR calculated using overall 6 months CGM data) is assumed to be 63% with same standard deviation as 16% and a correlation as 0.5. Thus, the hypothesis to be tested is:

$$H_0: \mu\text{TIR6m} - \mu\text{TIR baseline} = d_0$$

$$H_A: \mu\text{TIR6m} - \mu\text{TIR baseline} > d_0$$

where $d_0 = 3$ is the expected increase of TIR at 6 months. The sample size needed to demonstrate this hypothesis is 245 paired assessments per subject. The calculation is adjusted for loss-to-follow-up and protocol failures, including potential subjects with less than 70% of the time in Auto Mode with an assumption considering an attrition rate of 20%. The total number of subjects to be enrolled is 306.

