4.2.6. Satisfaction score on the DTSQs

- Objective: To evaluate the treatment satisfaction score on the DTSQs evaluated at baseline, 6 and 12 months.
- Endpoint: The different DTSQs versions will be used to assess satisfaction in the following populations:
 - DTSQs Adult (≥ 18 years old)
 - DTSQs Teen (13-17 years old)
 - DTSQs Parent (7-12 years old)

5. Investigation Plan

This study is a local, post-market, non-interventional, prospective, single-arm, multi-center, non-randomized study assessing the glycemic control effect, treatment satisfaction and the quality of

life of patients using MiniMed™ 780G System as per the standard care of practice. This study has a single-arm design which will recruit a maximum of 306 subjects in up to 32 sites in France. At the time of Clinical Investigational Plan finalization, the list of participating sites was not finalized. The complete list, which includes the name, position and address of the investigators responsible for conducting the study, will be available under separate cover and provided to the sites.

[figure not shown]
To avoid introduction of bias to the study results due to disproportionate enrollment, enrollment at any individual site shall not exceed 10% (30 subjects) of the total sample size. It is expected that sites enroll a minimum of 10 subjects per site.

Subject enrolled in this study (or his/her parent/legal representative in case of DTSQ and HFS for patients 7-12 years old) will be asked to complete the questionnaires DTSQ, DQoL (if patient is ≥ 13 years old) and HFS at baseline/enrollment visit and at 6- and 12- month follow-up visits.

The following measures are taken to minimize potential sources of bias:

- A multi-center design is used to ensure a representative sample of physicians providing the treatment and to reach a reasonable enrollment period.
- Site selection will be done per predefined selection criteria.
- Only physicians that have adequate documented experience in diabetes management will participate.
- Site training is performed according to the training & education plan set up for the pump use in order to assure full understanding and engagement to comply with the pump best utilization.
- Consecutive screening and enrollment will be encouraged and enforced as much as possible.

Figure 1: Study design overview

CareLink data uploads from the devices should be done as per clinical practice, i.e. once a week. CareLink data evaluation will be done every 3 months.

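### Protocol section 6 caps recruitment at 300, while protocol section 12.2 and the SAP require 306; the conflict is real but its effect on power is minor

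*Protocol*

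**What the plan says.** Protocol section 6 (Study Design) sets a ceiling: "This study has a single-arm design which will recruit a maximum of 300 subjects in up to 32 sites in France".

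Protocol section 12.2 derives 245 paired assessments, allows for 20% attrition and concludes: "The total number of subjects to be enrolled is 306". The statistics row of the protocol synopsis also gives 306. SAP section 6 repeats both the 245 and the 306.

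SAP section 5 carries the same design sentence as protocol section 6 but with the other number: "which will recruit a maximum of 306 subjects in up to 32 sites in France".

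The sample-size row of the synopsis is looser: "Approximately 300 patients (children and adults) in approximately 32 sites in France". Protocol section 10.11 adds that subjects who withdraw are not replaced.

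**The concern.** The protocol has a maximum of 300 in one section and a required enrolment of 306 in another. Both cannot be followed: stopping at 300 falls short of section 12.2, and going on to 306 exceeds section 6. The SAP has resolved this in favour of 306, so the two current documents also state different maxima.

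Enrolment is competitive across sites, so the overall stopping number is an operative figure. The calculation in section 12.2 also has no slack: 245 is the smallest number of pairs that reaches 90% power, so any cut in evaluable pairs takes the plan below the power it states. With no replacement of withdrawals, a loss at the cap could not be made up later.

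**Working it through.** **Inputs**

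- Error rate and power, protocol 12.2: "assuming a one-sided type I error rate of 0.05 and a power greater than 90" per cent.
- Effect, protocol 12.1: "Improvement in TIR of at least 3% points at 6 months compared to the baseline", that is 60% to 63%.
- Variability, protocol 12.2: 6-month TIR "is assumed to be 63% with same standard deviation as 16% and a correlation as 0.5".
- Attrition, protocol 12.2: 20%.
- Null value: 0. This is an assumption of the check. Both documents print the null as a difference of d0 with d0 = 3, but the stated 245 reproduces when a gain of 3 is tested against no change.

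**Step 1: reproduce the plan's figures**

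SD of the change = sqrt(2 × 16² × (1 − 0.5)) = sqrt(256) = 16.

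Normal approximation: n = ((1.645 + 1.282) × 16 / 3)² = 243.6, rounded up to 244.

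The exact paired t-test (noncentral t, one-sided 0.05) gives 89.90% power at n = 244 and 90.005% at n = 245. The required number is therefore 245, as stated.

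Enrolment: 245 / (1 − 0.20) = 306.25. The plan states 306; strict rounding up gives 307.

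**Step 2: apply the cap of 300**

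Pairs left: 300 × 0.80 = 240, which is 5 fewer than 245.

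Noncentrality: 3 × sqrt(240) / 16 = 2.905. Power is 89.5% with the t-test (89.6% with the normal approximation).

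| Enrolled | Pairs after 20% loss | Power at SD 16% (t-test) |
|---|---|---|
| 300 | 240 | 89.5% |
| 306 | 244.8 | 90.0% (at 245) |

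**Step 3: attrition at which the shortfall vanishes**

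1 − 245/300 = 18.3%. At or below this loss, 300 enrolled still gives 245 pairs.

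**Step 4: dependence on the SD**

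SAP section 6 prints an SD of 14% with the same correlation, so the SD of the change is 14. On that input 240 pairs give 95.2% power, and 188 pairs would be enough for 90%. The SAP's 245 therefore does not follow from its own 14%; it follows from the protocol's 16%. That is a separate inconsistency, but it means the power shortfall in step 2 exists only at 16%.

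**The case against.** The strongest reply is that this is one wrong figure in one sentence with no practical effect. Much of that stands.

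- **Size.** Five pairs and about half a percentage point of power would not change any conclusion.
- **The 20% is pessimistic for the primary analysis.** It also covers subjects with too little Auto Mode use, but the primary analysis is on the ITT set, which keeps them. Both documents use a dropout's data as far as they go, and 6-month TIR is calculated over the whole period since Auto Mode activation, so some dropouts may still provide a pair.
- **306 has a rounding gap of its own.** 306 × 0.8 = 244.8, so on a strict reading 306 does not secure 245 pairs either.

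Three stronger readings are tempting, and the documents support none of them.

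- A reader might infer that a trial obeying the cap is unable to reach its sample size. It can: 300 is enough if attrition is 18.3% or less, and 20% is only a planning assumption.
- A reader might multiply 32 sites by the per-site expectation ("It's expected that sites enroll a minimum of 10 subjects per site") to get 320, above both maxima. But section 6 gives 32 as an upper limit and the 10 as an expectation, so the product is not a planned total. Thirty sites at 10 each give exactly 300.
- A reader might take the site limit of 30 subjects, described as 10%, as proof that 300 is the intended total. But 30/306 = 9.8%, which also respects a 10% limit, and SAP section 5 keeps the same limit beside 306.

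The approximate 300 in the synopsis is likewise compatible with 306. What remains is the stated maximum in section 6, which cannot be read as rounding.

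**Conclusion.** The conflict is certain: a maximum of 300 in protocol section 6 against 306 in protocol section 12.2, the synopsis statistics row and SAP sections 5 and 6. It is a conflict between current texts.

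The consequence is minor. If the full 20% is lost, the cap leaves 240 pairs instead of 245 and 89.5% power instead of 90.0%, so the stated size and the stated power above 90% are both narrowly missed. This rests on SD 16%, correlation 0.5, a gain of 3 points tested against no change, and one-sided 0.05. It does not hold at attrition of 18.3% or less, nor at the SAP's SD of 14%. The study is not materially underpowered by the cap; the reason to act is that the operative maximum should be a single number.

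**What to change.** Change the maximum in protocol section 6 to 306, to agree with protocol section 12.2 and SAP sections 5 and 6. If 306.25 is rounded up, use 307 instead and carry it through every place where 306 now stands.

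If the sponsor prefers to keep 300, restate protocol section 12.2 and the synopsis statistics row as 240 evaluable pairs with about 89.5% power at SD 16%, and align the maximum in SAP section 5. Do not copy 89.5% into SAP section 6 as it stands: with its printed SD of 14%, 240 pairs give 95.2%. Reconcile 14% with 16% first, then align that section.

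The cost is a wording correction. Moving to 306 adds at most 6 subjects, already foreseen in section 12.2 (7 if 307 is used); keeping 300 costs about 0.5 points of stated power. If enrolment has already closed, which the documents do not show, state the maximum that was applied and explain any difference in the final report.
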